### Background:

For the majority of women with breast cancer (BrCA), radiation therapy (XRT) is critical for preventing local recurrence and improving breast preservation and survival.[1] XRT to the whole breast is a necessary component of breast conserving therapy and is standard of care following partial mastectomy; XRT has been shown to decrease locoregional recurrence by 2/3 and improve absolute survival by a minimum of 5% over lumpectomy alone.[1]

As the number of survivors has markedly increased, clinicians are now seeking to reduce treatmentrelated toxicities and inconveniences of treatment, namely the traditional 6 weeks of daily radiotherapy. Skin thickening, fibrosis, and edema are some of the most common acute and potentially long-term debilitating toxicities of BrCA XRT.[2, 3] During XRT, approximately 50% of patients develop significant cutaneous toxicity including moist skin desquamation, erythema, and hyperpigmentation.[2, 3]

Two recent studies have examined the role of hypofractionation (>2Gy per day with shorter overall treatment time) in the treatment of breast cancer.[4, 5] A recently published Phase III Canadian study randomized early stage BrCA patients to 42.5 Gy in 16 fractions (fxns) (2.66 Gy per day) or 50 Gy in 25 fxns (2 Gy per day) to the whole breast following lumpectomy and axillary lymph node dissection. [4] At 10 years, there was no difference in local control, survival, or cutaneous toxicity.[4] The UK START B study also randomized patients to 40 Gy in 15 fxns (2.66 Gy per day) or 50 Gy in 25 fractions (2 Gy per day) and found no difference in local control, survival, or cosmesis at 5 years.[5] Both studies successfully challenged the long held radiobiological belief that large daily fractions (>2 Gy per day) portends severe late normal tissue toxicity and unacceptable breast cosmesis following XRT. More recently, an updated analysis of the UK START trial was presented with 9.8 years of follow-up and there was still no difference in local control, survival or side effects between hypfractionated radiation and standard five weeks of XRT treatment.[6]

However, both the Canadian and UK studies included patient populations at relatively low risk of XRT-induced toxicity.[4, 5] Race, prior chemotherapy treatment, body habitus, and age have all been correlated with a patient's radiotherapy tolerance. More than 70% of participants in both hypofractionation studies were Caucasian and over the age of 50; fewer than 25% of patients received chemotherapy.[4, 5] It is known that African American women with BrCA experience more severe XRT-induced side effects than Caucasians, possibly contributing in part to poorer treatment adherence and worse outcome.[7-9] During and after XRT, African-Americans have worse cutaneous toxicity (edema, fibrosis, and pigmentation) than Caucasians (45% versus 10%, respectively). In addition, overall cosmesis, reflective of radiation-induced cutaneous toxicity, was good to excellent in 90% of Caucasians versus only 55% of African Americans following breast conserving treatment with XRT.[8] Negative perceptions of BrCA treatment including XRT may partially explain poor treatment

adherence rates in the African American community. Indeed, at our own institution, 26% of AAs with BrCA refused XRT in a recent study.[10] In addition to race, several studies have also found that patients heavily pre-treated with chemotherapy experience at least twice as much XRT induced skin desquamation and edema.[11-13] Moreover, women with larger breasts have higher rates of cutaneous toxicity due to the buildup of dose on the surface of the skin as the radiation beam tries to penetrate a large depth of tissue. For this reason, the Canadian study limited their enrollment to those women with less than 25cm of separation of the breast (the largest distance between the entry and exit point of the XRT beam on the breast). [4] Lastly, women less than age 50 have been found to have poorer cosmesis than older women following surgery and XRT.[7] Given the patient population treated in both the Canadian and UK studies, it is unclear if a shortened XRT regimen may be applied to a "high risk" patient (e.g. young patients previously treated with chemotherapy).

Furthermore, in the UK START study, post mastectomy patients were included as well as patients requiring regional nodal irradiation although only 15% of the enrolled patients were post-mastectomy patients and only 15% of the entire cohort needed regional nodal irradiation. Therefore, these patients at relatively higher risk for lymphedema/brachial plexopathy from XRT were under-represented in the UK START study. However, among the small number of patients treated with hypofractionated XRT to the regional lymph nodes (supraclavicular radiaton), there were no significant increases in lymphedema or brachial plexopathy compared to women treated with standard 5 weeks of XRT to the supraclavicular fossa.[6]

Additionally, a now standard boost dose to the lumpectomy cavity or chest wall, proven to significantly improve local control by 10% or greater in women less than 50 years of age [14-16], was not required in either arm of the Canadian or UK study. [4, 5] The boost dose has been shown to improve locoregional control in all patients by a minimum of 3% but appears to have the greatest impact in younger patients.[14-16] This boost dose has extended conventional XRT treatment from 5 (50 Gy in 25 fxns) to 6 weeks (60 Gy in 30 fxns) in the majority of patients treated within the United States.

At our institution, we have one of the largest experiences with simultaneous integrated boost (SIB) technique in patients with BrCA; we deliver 45 Gy in 25 fxns to the whole breast while treating the cavity simultaneously to a higher dose of 59.92 Gy in 25 fxns. Our published experience shows that at 3 years, our 5-week regimen is generally well tolerated with <1% of patients developing Grade 3 cutaneous toxicity and only 2.8% of patients recurring locally.[17] Our results are particularly important given that 39% of these patients were AA, 33% were premenopausal, 30% had breast separation >25cm, and 45% received chemotherapy, all factors associated with heightened skin toxicity from XRT. [17]

Seeking to shorten the treatment course further and improve convenience and treatment adherence, we propose to build upon our experience and the level I evidence advocating for hypofractionation in 15 days of treatment. Our proposed study will utilize the SIB technique with the whole breast treated to 40 Gy in 15 fractions and the cavity boosted simultaneously to 48 Gy in 15 fractions. Only one previous study has examined the feasibility of a similar fractionation with the whole breast treated to 40.5 Gy in 15 fractions, while the cavity is treated to 48 Gy.(20) At 1 year median follow-up time, 67% of patients had developed reversible grade 1-2 skin dermatitis and only 1 of 91 patients had recurred locoregionally.(20) However, only 1/3 of patients received chemotherapy and less than a quarter had large breast size. The majority of patients were over the age of 50 and 87% were Caucasian.(20) No study has examined the feasibility of a 15-day hypofractionated SIB XRT regimen in women at high risk for cutaneous toxicity (e.g. women below the age of 50, African American, and/or treated with chemotherapy). The unique patient population served by Emory will enable a study of SIB XRT given 12/13/2016

over 15 treatments. Quality of life measures (e.g. Multidimensional Fatigue inventory (MFI)[18], the Pittsburgh Sleep Quality Index (PSQI) [19], the perceived stress scale (PSS)[20], the Inventory of Depressive Symptomalogy-Self Reported (IDS-SR)[21], the Short-Form Health Survey (SF-36)(25) and the Godin Leisure Time Questionnaire (GLTEQ)(26)) which have been validated in multiple populations, will also be assessed in these patients to determine if 15 days of treatment is feasible.

### **Preliminary Data:**

Recent work from our group indicates that ultrasound tissue characterization (UTC) may objectively and reliably measure XRT-induced cutaneous toxicity in BrCA patients. UTC is a non-invasive technique developed by [name], PH.D.(co-Investigator), to delineate sub-resolution tissue features that are not visible by standard B-mode ultrasonography.[22, 23] From the UTC analysis, we can obtain quantitative parameters (skin thickness, Pearson coefficient, and midband fit value) characterizing the dermal, hypodermal, and subcutaneous tissue. These spectral parameters are related to structural tissue properties including skin thickening, fibrosis, and edema. [22, 23] In published work, the clinical assessments of XRT-induced skin toxicity correlate strongly with UTC measurements and objectively validate this measurement of skin toxicity.[23] However, interobserver subjective toxicity assessments have mild to moderate agreement. UTC would provide a reproducible way of characterizing toxicity. XRT-induced skin thickening increases with maximum thickness occurring at the completion of XRT. The thickening decreases significantly by 6 weeks post XRT in patients treated with a traditional 6 week course of XRT. We plan to use UTC to objectively quantify cutaneous toxicity during XRT in this study. Time points for analysis of cutaneous toxicity (baseline, fraction 15 of XRT and 2 - 5 weeks, 7 - 12 weeks, and 12 - 18 months post XRT) are based on these data.[23].

# Study Design:

Eighty breast cancer patients with Stage 0-III BrCA treated with breast conserving surgery or mastectomy and clear margins will be recruited to the study. Patients must have **one or more** of the following characteristics and be eligible for breast or chest wall with or without regional nodal radiotherapy:

1. Prior Chemotherapy for Breast Cancer

2. >25 cm of breast separation (the largest distance on an axial slice of the planning CT simulation scan between the entry and exit points of the radiation beam on the body)

- 3. Non-Caucasian Race
- 4. 4.
- 5. Requiring regional nodal irradiation without evidence of N3 disease

Because the above characteristics in isolation have been correlated with heightened levels of skin toxicity and/or were under-represented in previous trials of hypofractionated XRT, any patient fulfilling one of the above criteria, will be approached for enrollment in the study.

Males will be excluded.

To protect against possible side effects of radiation, women who are pregnant or nursing a child may not take part in this study.

Patients who have not received chemotherapy may start XRT up to 16 weeks after lumpectomy surgery. Patients who receive adjuvant chemotherapy after lumpectomy may start XRT up to 7 weeks after their last cycle of chemotherapy.

# **Dosimetry Guidelines for Hypofractionation SIB protocol for Breast Cancer**

Please plan breast treatments according to ICRU Guidelines.(19)

Treatment plans must be generated with heterogeneity corrections turned on.

Eligible patients are those being treated after lumpectomy or mastectomy.

#### Whole Breast or chest wall Treatment:

The whole breast or chest wall will be treated with tangents (modulated with either wedges or field-n-field technique) to a dose of **2.66 Gy per day x 15 fractions**.

The whole breast or chest wall should receive at least 95% of the prescribed dose. The whole breast or chest wall should receive less than 115%. No more than 8% of the whole breast should receive <95% of the prescribed dose.

5mm bolus may be used on the chest wall in postmastectomy patients at the discretion of the treating physician.

Central lung distance <2.5cm from chest wall to posterior edge of tangents Maximum heart distance <1.5cm from chest wall to posterior edge of tangents

#### Regional Nodal/ Supraclavicular Irradiation:

For patients requiring regional nodal irradiation, the physician will determine which lymph nodes are at risk and these targeted lymph nodes will be contoured (e.g. level I, II, III, and/or supraclavicular nodes and/or internal mammary lymph nodes).

The lymph nodes will be prescribed 2.66 Gy per day x 15 fractions and administered on the same day as the whole breast or chest wall treatment. The targeted regional lymph nodes should receive at least 90% of the prescribed dose. The targeted regional lymph nodes should receive less than 105% of the prescribed dose. If these dose constraints cannot be met, the treating physician has the option of decreasing the total dose to the targeted lymph nodes per day to 2.6 Gy per day x 15 fractions.

The supraclavicular nodes may be treated with an anterior oblique photon field or opposed oblique photon fields. The internal mammary nodes may be treated with deep tangents or an en face electron field.

### Simultaneous Integrated Boost to the Cavity Treatment:

The boost treatment will be given on the same days as the whole breast treatment.

The lumpectomy cavity + scar (in lumpectomy patients) or chest wall scar (mastectomy patients) will receive **0.54 Gy per day x 15 fractions**.

95% of the tumor bed volume should receive at least 95% of the prescribed dose.

Effort should be made to reduce treatment volume receiving more than 115% of the boost dose to less than 1%.

Electrons **or** photons may be used for the boost fields. It is up to the clinician to decide and will often be decided based upon the depth of the cavity.

If using photons (mini-tangents), for deep cavities, **margin is 1.5cm on cavity + scar** to field edge

Suggested photon fields for the boost are to use the same gantry angles from the initial whole breast fields with the same couch kick as the whole breast tangents. If the cavity is laterally located, kick the couch on the lateral tangent for a 3rd field 10 to 20 degrees. Leave the medial tangent alone. If the cavity is medially located, kick the couch 10 to 20 degrees from the initial couch kick on the medial tangent for the 3rd field. Leave the lateral tangent alone.

If using en face electrons for shallow cavities or chest wall, margin is **2.0 cm on cavity + scar** to block edge in all dimensions but posterior to the cavity volume in the case of breast conserving surgery patients.

\*\*\*Please note that if using electrons to boost the cavity or chest wall, this must be done on a non-breathold scan even when using breathold for whole breast tangent treatment for left sided tumors.

In addition to the port films, a cone beam CT scan will be done 1-2 times per week for localization of the tumor bed cavity. A cone beam CT scan is not necessary in post-mastectomy patients.

### **Dose Constraints to Normal Tissues:**

Heart:

Maximum heart distance <1.5cm on tangents or mean dose < 6 Gyor the heart volume receiving 13 Gy must be less than or equal to 10%. (V13Gy<10%)

Lung:

Central lung distance <2.5cm on tangents or the ipsilateral lung volume receiving 18 Gy must be less than or equal to 15%. ( $V_{18Gy} \le 15\%$ ), the contralateral lung volume receiving 2.5 Gy must be less than or equal to 15%. ( $V_{2.5Gy} \le 15\%$ ), or Total Lung V20 <36%

Contralateral breast dose: 12/13/2016

The contralateral mean breast dose must be < or equal to 3 Gy but aim should be less than 1 Gy

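### In a plan with a non-tangent nodal field, the tangent heart distance alone meets the heart line even if both heart dose limits fail; the ambiguous lung line has a similar gap

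*Protocol*

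**What the plan says.** All references are to the protocol unless stated.

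- **Heart** (Dose Constraints to Normal Tissues): "Maximum heart distance <1.5cm on tangents or mean dose < 6 Gyor the heart volume receiving 13 Gy", with that volume limited to 10%.
- **Lung** (same section): the line opens "Central lung distance <2.5cm on tangents or the ipsilateral lung volume receiving 18 Gy must be less than or equal to 15" per cent. After a comma it gives a contralateral limit (V2.5 at most 15%), and it ends "or Total Lung V20 <36" per cent.
- **Tangent section** (Whole Breast or chest wall Treatment): it lists "Central lung distance <2.5cm from chest wall to posterior edge of tangents" and "Maximum heart distance <1.5cm from chest wall to posterior edge of tangents", with no dose alternative to either.
- **Nodal section** (Regional Nodal/ Supraclavicular Irradiation): "The lymph nodes will be prescribed 2.66 Gy per day x 15 fractions and administered on the same day" as the breast or chest wall. On technique, "The supraclavicular nodes may be treated with an anterior oblique photon field or opposed oblique photon fields" and "The internal mammary nodes may be treated with deep tangents or an en face electron field". The section sets target coverage (at least 90%, under 105%) but no limit for heart or lung.
- **Safety monitoring** (Patients Requiring Regional Nodal Irradiation): lung and heart toxicity are two of the five adverse-event types collected. The stopping table covers only plexopathy, lymphedema and skin.

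**The concern.** A distance from the chest wall to the back edge of the tangents limits how much heart and lung the tangents cross. It says nothing about dose from an oblique supraclavicular field or an en face electron field over the internal mammary chain. Because the distance is joined to the dose limits by 'or', meeting it makes the heart dose limits unnecessary in plans whose extra fields it does not describe. Deep tangents are different: they are tangents, so the distance does describe them, and they are not part of this point.

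What is at stake is patient protection and the reading of any heart or lung event. Safety is in the primary objective. With no stopping boundary for heart or lung, the planning limits are the only numeric safeguard for those organs in the nodal cohort.

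**Working it through.** No sample size, power or alpha is involved, and the plan states no figure to reproduce. The check is one of logic, plus short arithmetic on the prescription.

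**Heart.** Let H = distance met, M = mean dose met, V = V13 met. The line is H or M or V. Of the 2 × 2 × 2 = 8 pass/fail patterns, 7 are accepted; only the pattern failing all three is rejected. If a non-tangent nodal field also required (M or V), 6 would be accepted. The one pattern newly rejected is distance met with both dose limits failed.

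**Lung.** Let A = distance, B = ipsilateral V18, C = contralateral V2.5, D = total lung V20. The printed order is A or B, C, or D, and the bare comma can mean 'and' or 'or'. With both printed 'or's kept there are five distinct readings. Two more replace the last 'or' with 'and'. The last column counts, out of 16 patterns, those accepted now that would fail an added check of (B and C) or D.

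| Reading | A alone passes | A and C pass with B and D failed | Newly rejected |
|---|---|---|---|
| A or B or C or D | yes | yes | 5 |
| A or (B and C) or D | yes | yes | 3 |
| A or (B and (C or D)) | yes | yes | 3 |
| ((A or B) and C) or D | no | yes | 1 |
| (A or B) and (C or D) | no | yes | 1 |
| A or (B and C and D), last 'or' changed | yes | yes | 3 |
| (A or B) and C and D, last 'or' changed | no | no | 0 |

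So all five readings that keep the printed 'or's leave no lung dose check beyond contralateral V2.5, and three of those five need no lung dose check at all. In the first row, 2 of the 5 newly rejected patterns have A failed: plans meeting only V18 or only contralateral V2.5.

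**The two sections together.** A plan over a distance but within the dose limits fails the tangent section and can pass the constraints section. The protocol does not say which governs. The gap remains either way: if the distances are compulsory, every accepted plan meets H, so the heart dose limits never decide anything.

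**Dose scale.** The nodal prescription is 15 × 2.66 = 39.9 Gy, or 15 × 2.6 = 39.0 Gy with the permitted reduction. Tissue counts toward heart V13 at 13/39.9 = 32.6% to 13/39.0 = 33.3% of prescription, and toward ipsilateral V18 at 18/39.9 = 45.1% to 18/39.0 = 46.2%. These are thresholds, not estimates of organ dose.

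**How tight is total lung V20 <36%?** Let s be the ipsilateral share of lung volume and c the contralateral V20. The ipsilateral V20 ceiling is (0.36 − c(1 − s))/s. The documents do not give s, so I assume 0.45 to 0.55. If contralateral V2.5 is met, c lies between 0 and 0.15.

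- s = 0.50: 72.0% at c = 0; 57.0% at c = 0.15.
- s = 0.45: 80.0% and 61.7%.
- s = 0.55: 65.5% and 53.2%.

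That is a loose backstop, so most of the gain from closing the gap is on the heart side.

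**The case against.** The strongest reply is that this is a drafting gap, not a missing safeguard. Measuring distances on the tangents and also giving a total-lung limit fits an intention that distances serve tangent-only plans and dose limits serve nodal plans. Planners may check heart dose routinely, and the protocol asks them to follow ICRU guidelines, which are not available here. All of that is plausible, but the text does not confine the distance option to tangent-only plans. If that was the intention, the added sentence only writes it down.

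Several narrower objections stand:

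- The heart gap matters mainly for an en face internal mammary field. That field is optional, so the number affected could be zero.
- The lung sentence is ambiguous, and its punctuation was recovered from a PDF. Counting readings does not say how likely any of them is.
- The lung gain is small, because a plan failing ipsilateral V18 can still pass on total lung V20.
- A single dose sum over tangents, nodes and boost is not always possible. The boost section requires an electron boost to be planned on a non-breath-hold scan even when left-sided tangents use breath-hold.
- Making the tangent section defer to the constraints section would loosen the distances for every patient, including those with no nodal field.

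**Conclusion.** The point holds and is minor. As written, a plan with a non-tangent nodal field can meet the heart line with mean dose and V13 both failed. The lung line has a similar gap on every reading that keeps its printed 'or's.

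The number affected is unknown. It is at most the 33 nodal patients enrolled (30 expected after dropout), and falls once nodes treated within tangents, and plans that meet the dose limits anyway, are set aside.

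A reader might infer that nodal patients received excess heart or lung dose, or that the trial's results are compromised. The documents support neither. They contain no organ-dose data, and they permit the dose check to be skipped without telling planners to skip it. No primary outcome, stopping rule or SAP analysis uses heart or lung dose. Nor can one say that the lung line certainly lacks a dose check: with the last 'or' taken as 'and', one reading requires both contralateral V2.5 and total lung V20.

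The conclusion rests on the printed wording and on the tangent distance not describing the supraclavicular or en face fields.

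**What to change.** Add one sentence to Dose Constraints to Normal Tissues, using only limits already there:

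> In any plan with a supraclavicular or en face internal mammary field, meeting a tangent distance alone is not sufficient; the summed tangent and nodal fields must also meet heart mean dose <6 Gy or V13 ≤10%, and either total lung V20 <36% or both ipsilateral V18 ≤15% and contralateral V2.5 ≤15%.

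Include the boost in the sum only when it is planned on the same scan. Where the boost section requires a separate non-breath-hold scan, report the boost's heart and lung dose separately.

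The investigators should confirm that this is the grouping of lung limits they meant. If they meant every item as an alternative, the sentence is stricter than their intent. Because it is an added requirement, it makes no plan acceptable that the constraints section rejects today.

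Leave the distances in the tangent section as they are, and have the investigators state which section governs when the two disagree.

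Cost: one sentence and one ruling by the investigators. Some nodal plans would need re-planning or would be logged as deviations. For patients already treated (the SAP dataset holds 75 cases, nodal and non-nodal not separated), only a descriptive count of nodal plans outside these limits is possible, beside the heart and lung adverse events. Even that depends on the dose-volume data having been kept: the protocol says radiation treatment is recorded but does not mention these figures.
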